# 7.3.1 Primary endpoint analyses

Primary analyses

Part I

The primary endpoint as specified in Section 2.1.2 will be derived according to BI standards. The analysis will be based on the treated set (TS) and will be descriptive in nature.

Part II

The primary endpoints (refer to Section 2.1.2) will be calculated according to the BI Standard Operating Procedure (SOP) 'Standards and processes for analyses performed within Clinical Pharmacokinetics/ Pharmacodynamics' (001-MCS-36-472).

The statistical model used for the analysis of the primary endpoints will be an analysis of variance (ANOVA) model on the logarithmic scale. That is, the PK endpoints will be log-transformed (natural logarithm) prior to fitting the ANOVA model. This model will include effects accounting for the following sources of variation: sequence, subjects within sequences, period and treatment. The effect 'subject within sequences' will be considered as random, whereas the other effects will be considered as fixed. The model is described by the following equation:

$$y_{ijkm} = \mu + \zeta_i + s_{im} + \pi_j + \tau_k + e_{ijkm}$$
, where

 $y_{ijkm}$  = logarithm of response measured on subject m in sequence i receiving treatment k in period j,

 $\mu$  = the overall mean,

 $\zeta_i$  = the ith sequence effect, i = 1, 2

 $s_{im}$  = the effect associated with the mth subject in the ith sequence, m = 1, 2, ..., ni

 $\pi_i$  = the jth period effect, j = 1, 2

$$\tau_k$$
 = the  $k^{th}$  treatment effect,  $k = 1, 2$ ,

 $e_{ijkm}$  = the random error associated with the  $m^{th}$  subject in sequence i who received treatment k in period j.

where  $s_{im} \sim N(0, \sigma_B^2)$  i. i. d. ,  $e_{ijkm} \sim N(0, \sigma_W^2)$  i.i.d. and  $s_{im}$ ,  $e_{ijkm}$  are independent random variables.

Point estimates for the ratios of the geometric means (test/reference) for the primary endpoints (see Section 2.1) and their two-sided 90% confidence intervals (CIs) will be provided.

For each endpoint, the difference between the expected means for log(T)-log(R) will be estimated by the difference in the corresponding adjusted means (Least Squares Means). Additionally their two-sided 90% confidence intervals will be calculated based on the residual error from the ANOVA and quantiles from the t-distribution. These quantities will then be back-transformed to the original scale to provide the point estimate and 90% CIs for each endpoint.

#### 7.3.2 Secondary endpoint analyses

#### Primary analyses

#### Part I:

The secondary endpoints (refer to Section 2.1.3) will be analysed descriptively. Analyses will be performed for the parent drug.

#### Part II:

The PK endpoint  $AUC_{0-\infty}$  will be assessed statistically using the same methods as described for the primary endpoint in part II.

Page 77 of 102

Proprietary confidential information © 2020 Boehringer Ingelheim International GmbH or one or more of its affiliated companies

# 7.3.4 Safety analyses

Safety will be assessed as defined by the endpoints listed in Section 2.1.2 and 2.2.2 based on the treated set (TS). Safety analyses will be descriptive in nature and will be based on BI standards.

Page 78 of 102

Proprietary confidential information © 2020 Boehringer Ingelheim International GmbH or one or more of its affiliated companies

For all analyses the treatment actually administered (= treatment at onset) to the subject will be used (any deviations from the randomised treatment will be discussed in the minutes of the Report Planning Meeting).

Treatments will be compared in a descriptive way. The placebo group in the safety evaluation will consist of all subjects treated with placebo, regardless of the dose group in which they were treated. The test treatment groups will be compared to the placebo group in a descriptive way. Tabulations of frequencies/proportions will be used for the evaluation of categorical (qualitative) data, and tabulations of descriptive statistics will be used to analyse continuous (quantitative) data.

Measurements (such as ECGs, vital signs, or laboratory parameters) or AEs will be assigned to treatments (see Section 4.1) based on the actual treatment at the planned time of the measurement or on the recorded time of AE onset (concept of treatment-emergent AEs). Therefore, measurements planned or AEs recorded prior to intake of trial medication (part I) or prior to *first* intake of trial medication (part II) will be assigned to the screening period, those between the (first) trial medication intake and end of REP (see Section 1.2.2) will be assigned to the treatment period. Events occurring after the REP but prior to trial termination date (part I and II) or prior to second or third treatment period (part II) will be assigned to 'follow-up'. These assignments including the corresponding time intervals will be defined in detail in the TSAP. Note that AEs occurring after the last per protocol contact but entered before database lock will be reported to Pharmacovigilance only and will not be captured in the trial database.

Additionally, further treatment intervals (called analysing treatments) may be defined in the TSAP in order to provide summary statistics for other than above periods, such as combined treatments, on-treatment totals, or periods without treatment effects (such as screening and post-study intervals).

Adverse events will be coded using the Medical Dictionary for Regulatory Activities (MedDRA). Frequency, severity, and causal relationship of AEs will be tabulated by treatment, system organ class and preferred term. SAEs, AESIs (see Section 5.2.5.1) and other significant AEs (according to ICH E3) will be listed separately.

Previous and concomitant therapies will be presented per treatment group without consideration of time intervals and treatment periods.

Laboratory data will be compared to their reference ranges. Values outside the reference range as well as possibly clinically significant values will be highlighted in the listings. Additionally, differences from baseline will be evaluated.

Vital signs or other safety-relevant data will be assessed with regard to possible on-treatment changes from baseline.

Part I only: The ECG variables QT, HR, QTcF, QTcB, PR, QRS, and RR obtained from the centralised evaluation of 12-lead ECG recordings will be the basis for the derivation of quantitative and categorical ECG endpoints. These endpoints and their analyses will be described in the TSAP.

c26547838-07 Trial Protocol Page 79 of 102

Proprietary confidential information © 2020 Boehringer Ingelheim International GmbH or one or more of its affiliated companies

#### 7.4 PRELIMINARY ANALYSES

#### Part I:

A preliminary analysis of PK parameters (AUC0-24 and Cmax of BI 706321), provided as individual values and geometric means, will be performed for each dose level prior to proceeding to the next higher level, with the exceptions described below under "Notes".

#### Notes:

- Data from at least 4 subjects on active treatment need to be available at the respective dose levels.
- For escalations up to Dose Group 3 (4 mg), preliminary PK data are not required. This is acceptable because the predicted plasma exposure parameters up to a dose of 4 mg (see Section 1.3.3.1) are sufficiently below the maximum acceptable exposure.

In contrast to the final PK calculations, the preliminary analysis will be based on planned sampling times rather than on actual times, regardless of whether actual times were within the time windows. Therefore, minor deviations may occur between preliminary and final results. The preliminary analysis will provide individual and mean concentration/effect-time profiles and summary statistics of individual values without subject identification information. The preliminary results will be distributed to the investigator and the trial team.

Depending on the results of available preliminary PK analyses and the tolerability and safety of the compound, changes to the dosing schedule (e.g., additional low or intermediate doses) and additional PK preliminary analysis may be performed if requested by the Clinical Trial Leader, the investigator, or Trial Clinical Pharmacokineticist. Preliminary PK results will not be reported in the CTR.

No inferential statistical interim analysis is planned. However, after completion of each dose group the investigator (or his or her deputy) is allowed to postpone further dose progression until a preliminary analysis of the data has been performed.

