#### 1.2.3 Clinical experience with BI 706321

In Part I of this study single rising doses up to 25 mg BI 706321 have been well tolerated by healthy subjects. The observed AEs did not follow any specific pattern of distribution and no dose dependency was observed. Neither SAE nor severe AE were observed. AEs reported in >1 subject on active treatment were coded as diarrhea (n=2, loose stool (8 mg) and watery stool (25 mg)) and nasopharyngitis (n=2, 0.6 and 15 mg). A total of 5 drug related AEs have been observed on active treatment: dry lips (0.3 mg), loose stool (8 mg), dizziness (15 mg), watery stool (25 mg) and generalized sensation of cold (25 mg). All these AEs were of mild intensity.

The "generalized sensation of cold" was accompanied by a slightly increased body temperature (37.4°C) and an increased CRP-value (35.4 mg/l). Beyond this no specific changes of laboratory parameters have been observed in the tested dose groups. Clinical monitoring did not show any relevant changes of ECG-parameters and vital signs.

c26547838-07 Trial Protocol Page 20 of 102

Proprietary confidential information © 2020 Boehringer Ingelheim International GmbH or one or more of its affiliated companies

Human pharmacokinetics was characterized by a slow absorption, a late  $t_{max}$ , a long elimination phase and a nearly dose proportional kinetics. Preliminary PK-data of dose groups tested in Part I of this study are displayed in the table below:

Table 1.2.3: 1 Preliminary PK Parameter given as gMean (tmax is given as median) after single oral doses of BI 706321 (Part I)

Dose (mg)	terminal t 1/2 (h)	$t_{max}(h)$	C max (nmol/l)	AUC 0-24 (nM*h)
0.3	8.53	6	0.388	5.17
0.6	17.7	6	0.781	11.5
1.2	24.0	6	1.02	15.2
2	22.8	6	2.27	34.8
4	35.8	5	5.19	69.8
8	37.5	4.5	11.8	166
15	37.8	4	24.6	320
25	13.1	3.5	41.1	559

Higher doses have not been tested in Part I of this study, because 2 subjects of the 25 mg dose group reached an AUC-value (741 and 759 nM\*h) that exceeded the maximum acceptable systemic exposure of this trial (693 nM\*h), meeting a defined stopping criterion (see Section 3.3.4.3).

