## 1.3.2 Maximum exposure and maximum dose for this trial

## 1.3.2.1 Maximum exposure

For a complete report of toxicity findings refer to the IB (c26475781).

Therefore, the following maximum acceptable systemic exposure of BI 706321 (exposure cap) for this trial is defined as follows:

Maximum acceptable systemic exposure of BI 706321 (exposure cap) for this trial:

○ Cmax: 86.1 nM

○ AUC0-24: 693 nM\*h

Page 23 of 102

Proprietary confidential information © 2020 Boehringer Ingelheim International GmbH or one or more of its affiliated companies

This exposure cap is defined for the expected (predicted) gMean values of a dose level as estimated based on preliminary PK data of preceding dose group(s). That means, a dose level will only be administered if expected gMean values for Cmax and AUC0-24 do not exceed these exposure values (see dose escalation stopping criterion 6 in Section 3.3.4.3).

In addition, due to inter-individual variability, actual systemic exposure in individual subjects may exceed these values. However, as soon as the actual observed exposure in one subject exceeds the maximum acceptable exposure, dose escalation will be stopped (see dose escalation stopping criterion 7 in Section 3.3.4.3).

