## 1.3.3.3 Preliminary PK analysis

Dose escalation will be guided by preliminary PK analysis with the following aims:

- Ascertaining that adequate exposures are reached in this trial as a basis for further development of BI 706321,

\*\* added with global amendment No. 1; dose group numbering follows logistical reasons (alignment with other trial documentation)

\*\*\* added with global CTP amendment 3; dose group numbering follows logistical reasons

<sup>a predictions are based on pre-clinical data

<sup>b estimations are based on linear extrapolation of 1.2 mg preliminary PK data

6547838-07 Trial Protocol Page 28 of 102

Proprietary confidential information © 2020 Boehringer Ingelheim International GmbH or one or more of its affiliated companies

- Ascertaining that the expected gMean exposure values of the next dose group do not exceed the maximum acceptable exposure in order to protect subject's safety, and

- Ascertaining that dose escalation is stopped in case observed exposure values of a single subject exceed the maximum acceptable exposure.

For details, see Sections 3.3.4.3 and 7.4.

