# 3. DESCRIPTION OF DESIGN AND TRIAL POPULATION

#### 3.1 OVERALL TRIAL DESIGN AND PLAN

#### Part I:

This single-rising dose trial is designed as single-blind, randomised, and placebo-controlled within parallel dose groups.

It is planned to include a total of 64 healthy male subjects in the trial. The subjects will be assigned to 8 groups consisting of 8 subjects per group; the groups will be dosed sequentially (see Table 3.1:1). The investigator is allowed to alter the scheduled dose groups (e.g., add low and/or intermediate dose groups) on the basis of experience gained during the study (for instance, based on preliminary PK data), provided the planned and approved highest dose is not exceeded. Thus, the actual number of subjects entered may be more than 64, but is not to exceed 80. Such changes may be implemented via non-substantial CTP amendments.

Within each dose group, 6 subjects will receive BI 706321 and 2 will receive placebo. Only one dose is tested within each dose group. For safety reasons, each dose group will consist of 3 cohorts. The trial medication will be administered in the following order:

- Cohort 1: 1 subject on active treatment and 1 subject on placebo (in total 2 subjects)
- Cohort 2: 2 subjects on active treatment (in total 2 subjects)
- Cohort 3: randomised 3 subjects on active treatment and 1 subject on placebo (in total 4 subjects)

There will be at least 10 min between treatment of the sentinel subject, i.e. the first subject of cohort 1 (BI 706321) and the second subject of cohort 1 (placebo).

Cohort 2 will be treated not earlier than 22 hours later (minimum time interval between 1st subject of cohort 1 [sentinel subject] and 1st subject of cohort 2). This is expected to be sufficient to detect relevant acute effects of BI 706321 in the sentinel subject prior to exposing more volunteers to BI 706321 at the respective dose level. In cohort 2, a time interval of at least 10 min will be maintained between dosings of individual subjects (both treated with BI 706321).

Cohort 3 will be treated not earlier than 22 hours later (minimum time interval between 1st subject of cohort 2 and 1st subject of cohort 3). In cohort 3, a time interval of at least 10 min will be maintained between dosings of individual subjects (3 treated with BI 706321, 1 treated with placebo; randomized order).

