Although no formal Safety Review meeting will take place within a given dose group, safety will be continuously monitored during this trial, and an individual will only be dosed in the absence of any safety concern (i.e. no dose-limiting events occurred) and if none of the prespecified trial-specific stopping criteria have been met (refer to Section 3.3.4.3).

\*\* Added with global CTP amendment 1. Dose group numbering follows logistical reasons (alignment with other trial documentation).

\*\* Added with global CTP amendment 3. Dose group numbering follows logistical reasons.

Proprietary confidential information © 2020 Boehringer Ingelheim International GmbH or one or more of its affiliated companies

At minimum, data from 5 subjects on active drug need to be available for escalation to a higher dose. For the minimum dataset with regards to preliminary PK data, see Section 7.4. The minimum data set for review consists of the following:

- AEs in the current and preceding dose groups up to at least 24 h post dosing, including clinically relevant findings from ancillary safety testing listed below (Note: AEs may be ongoing at the time of Safety Reviews and AE information may be subject to change prior to Database Lock)
- Results from 12-lead ECG and the assessment of the continuous ECG monitoring in the current and preceding dose groups up to at least 24 h post dosing
- Vital signs in the current and preceding dose groups up to at least 24 h post dosing
- Clinical laboratory tests in the current and preceding dose groups up to at least 24 h post dosing (for escalation to dose groups up to 4 mg [inclusive]) or up to at least Visit 2 Day 8 (for escalation to dose groups higher than 4 mg).
- Preliminary PK data for the selected time as per Section 7.4
- Check of criteria for stopping subject treatment as per Section 3.3.4.1

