#### 3.3.4.3 Discontinuation of the trial by the sponsor

Boehringer Ingelheim reserves the right to discontinue the trial at any time for any of the following reasons:

- 1. Failure to meet expected enrolment goals overall or at a particular trial site
- 2. New toxicological findings, serious adverse events, or any safety information invalidating the earlier positive benefit-risk assessment.
- 3. Violation of GCP or the CTP impairing the appropriate conduct of the trial.
- 4. The sponsor decides to discontinue the further development of the investigational product
- 5. Dose escalation will be stopped if at least 2 subjects on active treatment at one dose level have relevant individual QT prolongations, i.e. absolute QTc greater than 500 ms, as confirmed by a repeat ECG recording, or a QTc increase of greater than 60 ms from baseline mean, as confirmed by a repeat ECG recording
- 6. Dose escalation will be stopped if the estimated gMean exposure of the next higher dose level is expected to exceed a Cmax of 86.1 nM or an AUC0-24 of 693 nM\*h. In this case, one or two additional dose levels lower than the planned next dose level may be given, as long as the expected gMean exposure values of the interim dose do not exceed these exposure thresholds. Estimation will be done based on preliminary PK results of preceding dose groups (see Section 7.4)
- 7. Dose escalation will be stopped if the observed Cmax or AUC0-24 of at least 1 subject of one dose group exceeds the exposure thresholds defined in dose escalation stopping criterion 6 above.
- 8. Occurrence of severe non-serious adverse events considered as drug-related by the investigator in 2 subjects of the same dose group or occurrence of at least one drug-related serious adverse event. Moreover, dose escalation will be terminated if more than 3 of the actively dosed subjects at one dose level show drug-related and clinically relevant adverse events of at least moderate intensity.

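### Section 7.4 accepts PK from 4 of the 6 active subjects for escalation above 4 mg, which is too few to ascertain that no single subject has exceeded the exposure cap

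*Protocol*

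**What the plan says.** All references are to the protocol; the SAP does not address the point.

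- **Group size (Section 3.1, Part I).** "Within each dose group, 6 subjects will receive BI 706321 and 2 will receive placebo".
- **PK minimum (Section 7.4, Notes).** "Data from at least 4 subjects on active treatment need to be available at the respective dose levels". No preliminary PK is needed for steps up to and including 4 mg.
- **General minimum (Section 3.1).** "At minimum, data from 5 subjects on active drug need to be available for escalation to a higher dose". The next sentence takes PK out of that figure: "For the minimum dataset with regards to preliminary PK data, see Section 7.4".
- **Criterion 6 (Section 3.3.4.3).** Escalation stops if the projected geometric mean of the next dose exceeds 86.1 nM (Cmax) or 693 nM*h (AUC0-24).
- **Criterion 7 (Section 3.3.4.3).** Escalation stops if the observed Cmax or AUC0-24 "of at least 1 subject of one dose group exceeds the exposure thresholds defined in dose escalation stopping criterion 6 above". Section 1.3.2.1 says the same: "as soon as the actual observed exposure in one subject exceeds the maximum acceptable exposure, dose escalation will be stopped". Section 1.4.4 lists this rule among the safety measures.
- **Aim of the preliminary PK analysis (Section 1.3.3.3).** "Ascertaining that dose escalation is stopped in case observed exposure values of a single subject exceed the maximum acceptable exposure".
- **What happened (Section 1.2.3).** Doses above 25 mg were not tested "because 2 subjects of the 25 mg dose group reached an AUC-value" above the cap (741 and 759 nM*h).

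**The concern.** Criteria 6 and 7 ask different questions of the same data. Criterion 6 concerns a geometric mean, which can be estimated from a subset of the group with some loss of precision. Criterion 7 concerns whether any member of the group is above the cap, and a subset cannot answer that in the negative. Section 7.4 gives one minimum for both, and it suits only the first.

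A team that follows Section 7.4 exactly may therefore record criterion 7 as not met while up to 2 actively dosed subjects have no exposure result. The next, higher dose could then be started although a subject at the current dose is already above the cap. This is a first-in-man escalation in healthy volunteers, and the single-subject rule is one of its stated protections. Preliminary PK results are not reported in the clinical trial report (Section 7.4), so that report would not show whose profile was outstanding at a decision.

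**Working it through.** **Plan's own figures.** Part I: 8 groups x 8 subjects = 64, as stated in Section 7.7. Active subjects per group: 1 + 2 + 3 = 6 over the three cohorts, as stated in Section 3.1. The documents give no detection probability for criterion 7.

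**Does another section raise the 4?** Section 3.1 does not, because it defers to Section 7.4 for PK. Section 7.4 permits the investigator to postpone progression but does not require it. The interval of at least 10 days above 4 mg makes complete data likely but does not make them a condition.

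**Chance that exceeders are not yet seen.** Suppose k of the 6 active subjects exceed the cap and n profiles are available, with the missing ones random. Then

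P(none of the k is among the n) = C(6-k, n) / C(6, n).

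| Profiles available | One exceeder (k = 1) | Two exceeders (k = 2) |
|---|---|---|
| 4 | 5/15 = 33.3% | 1/15 = 6.7% |
| 5 | 1/6 = 16.7% | 0% |
| 6 | 0% | 0% |

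**Sensitivity without assuming that an exceeder exists.** The documents give no between-subject variability, so a geometric CV of 15% to 50% is assumed, with lognormal AUC0-24. With sigma = sqrt(ln(1 + gCV^2)), the chance that one subject exceeds the cap is p = 1 - Phi(ln(693/gMean)/sigma). The chance that criterion 7 is met among the 6 but not among the n seen is (1-p)^n - (1-p)^6. The geometric means come from Table 1.2.3: 1.

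| Dose | gMean AUC0-24 (nM*h) | 4 profiles | 5 profiles |
|---|---|---|---|
| 15 mg | 320 | 0.0% to 8.1% | 0.0% to 3.9% |
| 25 mg | 559 | 10.6% to 14.8% | 4.6% to 6.6% |

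At 15 mg and a gCV of 30% the figure with 4 profiles is 0.8%. At 8 mg (gMean 166) it is at most about 0.25%, and at 4 mg (gMean 69.8) it is practically zero. PK at 4, 8 and 15 mg preceded the steps actually taken under this rule.

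**Would criterion 6 have caught the 25 mg case?** Assume dose-proportional scaling to 40 mg (factor 1.6), and that 559 is the geometric mean of all 6. All six: 559 x 1.6 = 894 nM*h. Without the two exceeders, the other four have geometric mean (559^6 / (741 x 759))^(1/4), about 483, and 483 x 1.6 is about 772 nM*h. Both exceed 693, so criterion 6 would have blocked 40 mg. It would still have allowed one or two lower interim levels with a projected geometric mean under the threshold, so it does not replace criterion 7.

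**The case against.** The strongest reply is that nothing here is contradictory. Criterion 7 and Sections 1.3.2.1 and 1.3.3.3 all act on observed exposure, and a profile not yet available has not been observed. A minimum data set and a trigger on observed values can both be obeyed. That stands: a reader might infer that the passages cannot be followed together, and the documents do not support it. What does not follow is that 4 profiles achieve the aim in Section 1.3.3.3. Ascertaining the single-subject stop requires knowing about each subject.

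Second, an outstanding exceeder is delayed, not lost. Section 1.3.2.1 stops escalation as soon as one subject exceeds the cap, and Section 3.1 allows an individual to be dosed only if no stopping criterion has been met. The next group also starts with a single active subject, with at least 22 hours before cohort 2. This stands and limits the consequence to subjects dosed before the late result arrives.

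Third, 4 is a floor. AUC0-24 needs only 24 hours of sampling, above 4 mg the groups are at least 10 days apart, and laboratory data to Day 8 are required anyway. All 6 profiles may usually be at hand, though no section requires them.

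Fourth, a reader might take the 4 in Section 7.4 against the 5 in Section 3.1 as a leftover from Amendment 1. The amendment log says that change concerned safety and tolerability data and does not list Section 7.4, so the difference is not evidence of an oversight.

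Finally, Part I escalation is over and the rule worked. That stands as well. Part II gives fixed 4 mg doses without escalation.

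**Conclusion.** The point holds as a gap between the PK minimum and the stated aim. For Part I escalations above 4 mg, meeting the minimum in Section 7.4 does not show that criterion 7 is unmet, and no other section supplies the missing condition.

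The 33% and 6.7% figures assume that an exceeder exists, that exactly 4 profiles are available, and that the missing ones are random. The unconditional figures also rest on the assumed gCV range. They are negligible at 4 and 8 mg, at most about 8% at 15 mg, and 10.6% to 14.8% at 25 mg, again at the floor of 4.

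A reader might infer that a subject above the cap was overlooked in this trial. Section 1.2.3 shows the opposite: criterion 7 was detected at 25 mg and higher doses were not tested. Nor does the rule now govern a live escalation. Groups 7 and 8 remain in the tables, but they need a substantial amendment and escalation has stopped. The point matters for how the Part I rule was written, and for those groups if they were ever opened by amendment.

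**What to change.** Reconcile Sections 7.4, 3.1, 1.3.3.3 and criterion 7 in Section 3.3.4.3. The text should state which active subjects' PK must be available before criterion 7 is recorded as not met, separately from the data needed for the geometric-mean projection in criterion 6. Which rule to adopt is for the sponsor to decide.

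The cost is about one sentence in Section 7.4 and matching wording in the other sections. No extra sampling is needed, because PK blood sampling is already scheduled for these groups. Depending on the rule chosen, the downside is an occasional short delay when a profile is late.
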